At VCU Health system, Anesthesiologists have been successfully using LMA (General Anesthesia) for ablation in PAF in eligible patients for over five years. The investigators are proposing a randomized, single blind study to evaluate the use of LMA versus ETT in this patient population. A concurrent retrospective study will be conducted to evaluate the last two years data of outcomes in this patient population at VCU. The investigators wish to do a prospective study to reduce bias, as the patients who have greater comorbidities are more likely to have ETT for an esthesia, and we believe this will skew the retrospective data when it is collected. The LMA used at VCU Health are LMA Supreme (Teleflex Medicals, Ireland). The study is designed as a non-inferiority study with a primary outcome of procedure length.

Secondary outcomes will include flouroscopy duration, total anesthesia time, total intra- and post- procedure opioids and ionotropes/pressors/chronotropes, patient satisfaction, PAF recurrence.

Briefly describe the study design, including all interventions or interactions with research participants and access to identifiable data. Use lay language whenever possible.

This will be a prospective, randomized single blind study comparing the use of general anesthesia with endotracheal tube versus laryngeal mask airway in patients undergoing abiation for paroxysmal atrial fibrillation. Patients will be consented the morning of the procedure and will be conducted only by study personnel. All patient identifiers will be stored in a separate, password protected document from data set. Patients will be randomized, data collected and stored in the secure REDCAP database. REDCap database randomization software will be used to randomize patients into one of the two study groups. Patients will be randomized after they sign informed consent the morning of the procedure. Randomization will be done by study personnel using REDCap and verbally conveyed to anesthesia provider that morning of procedure. The minimum necessary study personnel will have access to patient identifiers.

Power analysis: Estimated mean procedure time 3 hours, range 1.5-4.5 hours, standard deviation 0.9, n = 82 to detect 0.5 hour margin of non-inferiority between the two groups. Including 5% drop-outs, final n=87. Goal enrollment 44 patients per group.

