4. If applicable, upload a Co	ost Analysis form here:
: HM20007902	View: SF - Standard of Care Vs. Research Costs

Standard of Care Vs. Research Costs

1. *Describe any procedures, therapy, lab work, x-rays, drugs, or devices, etc that are considered standard of care and will be charged to the participant or their insurance:

All associated procedures involving anesthesia, abiation, hospitalization, post procedure holter monitors and post procedure office visits are considered standard of care and will be charged to participant and their insurance.

2. Describe the process to determine whether participants' insurance will cover the expenses: Patients will have the procedure and all associated expenses submitted to insurance as standard of care.

ID: HM20007902

View: SF - Compensation

Compensation

- Describe any compensation that will be provided including:
 Items such as parking/transportation

 - total monetary amount
 - type (e.g., gift card, cash, check, merchandise, drawing, extra class credit)
 how it will be disbursed:

No compensation.

2. If compensation will be pro-rated, explain the payment schedule:

ID: HM20007902

View: SF - Risks, Discomforts, Potential Harms and Benefits

Risks, Discomforts, Potential Harms and Benefits

- Describe the risks to participants associated with this study:

 physical, psychological, social, legal, financial, and other risks
 - seriousness of given risks
 - probability or likelihood of given risks

The risks of LMA airway management in atrial fibrillation abiation are: gastric aspiration, intraoral trauma, intraoral nerve paisies, largynospasm, incorrect placement, need for conversion to ETT, sore throat, pulmonary edema, bronchoconstriction

The risks of ETT airway management in atrial fibriliation abiation are: oral injury, dental injury, incorrect placement, hoarseness, sore throat, laryngospasm, laryngeal injury, difficulty swallowing.

There is a potential risk of loss of condifentiality.

2. Describe how the risks / harms will be minimized:

Risks/harms will be minimized as patient data will be carefully managed and accessible by minimum necessary study personnel. Risks are minimized as both groups will have anesthetic plans that have been proven safe and standard of care in a wide variety of clinical

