- If the disclosure of any of the information obtained during the study would place the individual at risk for harm (legal, reputation, emotional etc.) and the information will be recorded so that the individual could be identified, explain the protections that will be put in place to decrease the risk of disclosure:
- 4. * The Code of Virginia requires that most medical personnel and all employees of institutions of higher education report suspected child/elder abuse or neglect. Is it likely investigators could discover information that would require mandatory reporting by the investigators or staff:
 - Yes
 - No
- 5. Is it likely investigators could discover a participant's previously unknown condition (eg disease, suicidal thoughts, wrong paternity) or if a participant is engaging in illegal activities:
 - Yes
 - No
- 6. If yes, explain how and when such a discovery will be handled:
- 7. Describe any potential risks or harms to a community or a specific population based on study findings: There is minimal to no risk or harms to a community or specific population based on study findings.
- Pescribe criteria for withdrawing an individual participant from the study; such as safety or toxicity concerns, emotional distress, inability to comply with the protocol, etc.:

Participants will be withdrawn from the study if they are converted from their initial randomization. They will also be withdrawn if they request to be removed from study. Patients who do not complete all the post discharge holter monitor evaluations will be kept in the study, and the missed data fields will not be evaluated for that specific patients

- Summarize any pre-specified criteria for stopping or changing the study protocol due to safety concerns:
 No specified criteria for stopping or changing study protocol for safety concerns.
- 10. Where appropriate, discuss provisions for ensuring necessary medical, professional, or psychological intervention in the event of adverse events to the subjects:
- 11. Describe any potential for direct benefits to participants in this study: Participants in this study have potential for benefits of possibly fewer side effects, while also having a similar outcome with regards to

12. * Describe the scientific benefit or importance of the knowledge to be gained: The scientific benefit of knowing if the use of LMA is associated with similar (non-inferior) outcome in term of procedure length and

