determining if the side effects and patient satisfaction are superior could improve the anesthetic care of patients undergoing abiation of

- 13. If applicable, describe alternatives (research or non-research) that are available to potential participants if they choose not to participate in this study:
- 14. Indicate if this study will have a Data Safety Monitoring Board (DSMB) or a Data Safety Monitoring Plan (DSMP): [Required for all Full Review studies)

DSMB Review Required
✓ DSMP Required
Not Required

ID: HM20007902

View: SF - DSMP Details

DSMP Details

1. Describe your Data Safety Monitoring Plan for monitoring the data collected to ensure the safety of participants. Data collection will be done in a timely manner, with initial data input within a week of each visit. After the first 25 patients are enrolled an Interim analysis of primary outcomes as well as adverse outcomes will be done to determine if there is an association between either group and increased incidence of adverse outcomes. If an association is seen the IRB will be notified and the project design reevaluated.

View: SF - Consent Qualifiers ID: HM20007902

Consent Qualifiers

- 1. Are you submitting your study as exempt and therefore no consent is required:

No

ID: HM20007902

View: SF - Consent Groups

Consent Groups

1. " List all consent groups:

Group	Types	Waivers	Roles	Roles Consent	Coercion	Decision	Status Change
				Other			Onlang
Qualified Patients	Consent by	Walvers	Principal Investigator	Consent will be obtained in the	approached by study personnel and given facts of r study, no coercion will be utilized to encourage	e Patients will be y given from time approached by study personnel unti medications which may after decision making ability are given. Approximately 30 minutes to 1 hour	
	Participant	Requested	Co/Sub- Investigator	preoperative holding s area prior to procedure. Consent			ı
			Research Coordinator	will be obtained prior to patient receiving			
			Research Assistant	any medications which would potentially interfere			
			Trainee/Student			prior to procedure start.	
Patient Screening	None of the Above (select	Walver of Some or	Principal Investigator	No consent will be obtained	No consent will be obtained	No consent will be obatined	
	walver below)	All Elements of Consent	Co/Sub- Investigator				
		or consent	Research Coordinator				
			Trainee/Student				

2. Upload any consent / assent documents:

ID: HM20007902

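### The rule that withdraws converted patients can drop LMA conversions, and adverse events in those patients, from the 25-patient safety look

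*Combined protocol and SAP*

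**What the plan says.** All references are to the combined protocol and SAP.

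- **SF - DSMP Details, item 1** sets the look: "After the first 25 patients are enrolled an Interim analysis of primary outcomes as well as adverse outcomes will be done". Its stated purpose is "to determine if there is an association between either group and increased incidence of adverse outcomes", and the consequence is "If an association is seen the IRB will be notified and the project design reevaluated". The readable text describes no other comparison of safety by group.
- **Risks, Discomforts, Potential Harms and Benefits, item 1** includes "need for conversion to ETT" among the LMA risks. The ETT list has no matching entry.
- **Same section, the item on criteria for withdrawing a participant** says: "Participants will be withdrawn from the study if they are converted from their initial randomization". It treats incomplete monitoring differently: "Patients who do not complete all the post discharge holter monitor evaluations will be kept in the study".
- **Same section, the item on stopping criteria** says: "No specified criteria for stopping or changing study protocol for safety concerns".
- **HIPAA, item 1** lists the data to be collected. Airway trauma and aspiration are taken from clinical notes. The readable list has no item for conversion during the procedure.
- **Research Description** states: "The study is designed as a non-inferiority study with a primary outcome of procedure length". The outcome named alongside adverse outcomes in the interim sentence is therefore procedure time.

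**The concern.** The look exists to find out whether either airway goes with more adverse outcomes. Conversion is a harm that the form itself attributes to the LMA, and a patient whose LMA fails may also be one in whom other airway events occur. If conversion takes a patient out of the study, both the conversion and any accompanying events can leave the LMA column before the two groups are compared. The loss depends on what happened to the patient after randomisation, and the form's own risk lists suggest that it falls mainly on one arm.

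At stake is whether a signal against the LMA could be understated at the only planned point where the design might be re-evaluated for safety.

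**Working it through.** **1. The passages side by side.** The withdrawal item has two categories: converted patients leave, and patients with missed Holter visits stay. The authors therefore distinguished being withdrawn from being kept with some data missing, and put conversions in the first category. The DSMP item does not say that converted patients are nevertheless counted. The data list in the HIPAA section has no readable field that would capture a conversion during the procedure.

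**2. The plan's own sample size.** Inputs from the power analysis in Research Description are SD 0.9 h, margin 0.5 h and two equal groups. Alpha and power are not stated. Taking one-sided 5%, 80% power and no true difference:

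- n per arm = 2 × (1.645 + 0.842)² × 0.9² / 0.5² = 40.1, rounded up to 41, so 82 in total. This matches the plan.
- 82 / 0.95 = 86.3, rounded up to 87. This also matches, and allows 87 − 82 = 5 drop-outs.

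The sample size is used below only for the drop-out allowance.

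**3. Size of the look.** 25/87 = 29% of planned enrolment. With 1:1 allocation the split is assumed to be 12 and 13.

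**4. Weight of one patient.** 1/13 = 7.7% and 1/12 = 8.3% of the LMA arm. For example, if one converted patient is the only event among 13 LMA patients, the rate is 1/13 = 7.7% with that patient counted and 0/12 = 0% with that patient removed.

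**5. Chance that the issue arises by the look.** No conversion rate is given, so three are assumed. The highest is a deliberate extreme in which all 5 allowed drop-outs are LMA conversions among 44 patients: 5/44 = 11.4%. For m LMA patients and conversion rate c, P(at least one) = 1 − (1 − c)^m.

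| Assumed rate c | m = 12 | m = 13 |
|---|---|---|
| 2% | 0.215 | 0.231 |
| 5% | 0.460 | 0.487 |
| 11.4% | 0.765 | 0.792 |

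The range is therefore about 22% to 79%, and it depends almost entirely on a rate that the documents do not supply.

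**The case against.** **Withdrawal need not mean deletion.** The form does not define the term as discarding data already collected. The look is based on the first 25 patients enrolled, and a converted patient has been enrolled. Airway trauma and aspiration come from routine notes that exist whether or not the patient stays in the study. A reader might infer that the plan discards these events. It does not say so, and a reading in which they are counted is open. This stands, and it is why the point is only that the look can lose them.

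**Some relevant text is damaged.** The paragraph on LMA placement in Research Description breaks off, and the airway-trauma item in the HIPAA section is partly illegible. Either might have mentioned failed placement or conversion. The statement that no conversion item exists is therefore limited to the readable text.

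**The rule applies to both arms.** That is correct. The direction of any bias is inferred from conversion being listed under LMA risks alone.

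**A look this small might not change its conclusion anyway.** With 13 LMA and 12 ETT patients and no ETT events, a two-sided Fisher test needs five LMA events to fall below 0.05 (p = 0.039; four give p = 0.096). Losing one or two patients would often leave such a test where it was. This also stands. However, the plan sets no threshold for an association, so the tabulated counts may be read descriptively, and those counts would be incomplete.

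**Type I error.** Because procedure time is in the interim sentence, a reader might infer an unadjusted extra test of the primary hypothesis. The documents do not support that. No early success claim is planned, the only trigger is an adverse-outcome association, and no passage proposes changing the margin, sample size or endpoint in response to procedure times. Study personnel can in any case already see both arm and procedure time.

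**Conclusion.** The concern holds as a minor one. As written, the withdrawal rule can remove LMA conversions, and adverse events in the converted patients, from the only planned by-group safety comparison. The LMA arm could then look safer than it was. Each omitted patient is about 8 percentage points of an arm of 12 to 13, and the chance that at least one such patient exists by the look is 22% to 79%.

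This rests on three assumptions: a 12 v 13 split, conversion rates of 2% to 11% that are not in the documents, and a reading of withdrawal that the text permits but does not compel. It is not shown that events would in fact be discarded or that the look would reach a different conclusion.

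The inclusion of procedure length in a look with only a safety purpose is a mismatch of wording. No inflation of type I error is claimed.

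**What to change.** 1. In SF - DSMP Details, item 1, state that the look tabulates adverse events and airway conversions for all randomised patients by assigned arm, including those converted from their assigned airway.
2. Add conversion during the procedure, in either direction, as a recorded data item.
3. Reconcile the withdrawal item in the Risks section with this, so that a converted patient's events and conversion remain in the safety tabulation.
4. As a secondary wording change, delete the reference to primary outcomes from the interim sentence, since no use is stated for them there.

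The cost is wording in two form fields and one extra recorded item. The planned sample size does not change. The team gives up a formal early comparison of procedure time that has no stated role. No clinical stopping or conversion rule is proposed.

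### The safety monitoring plan rests on one look at 25 patients and an undefined association, with no planned by-arm review for the remaining 62 to 63 patients until the end-of-study analysis

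*Combined protocol and SAP*

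**What the plan says.** DSMP Details, item 1, promises data entry within a week of each visit and then one review: "After the first 25 patients are enrolled an Interim analysis of primary outcomes as well as adverse outcomes will be done". On the safety side, an analysis of "adverse outcomes will be done to determine if there is an association between either group and increased incidence of adverse outcomes". The consequence is: "If an association is seen the IRB will be notified and the project design reevaluated". The item gives no test, threshold, list of events or grading of seriousness, and describes no later look.

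Risks, Discomforts, Potential Harms and Benefits, item 9, which asks for pre-specified safety criteria, answers: "No specified criteria for stopping or changing study protocol for safety concerns". Item 8 of the same section withdraws participants who are converted from their randomised airway, and item 1 lists conversion to a tube among the risks of the LMA.

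Planned enrolment comes from the power analysis (Research Description, item 4, repeated under Study Population): "Including 5% drop-outs, final n=87. Goal enrollment 44 patients per group". The HIPAA section, item 1, already lists airway trauma, aspiration events, nausea and emesis as separate data items. Side effects also appear in the secondary hypothesis, which is an end-of-study comparison.

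**The concern.** A monitoring plan should tell staff and the IRB what will be looked at, when, and what obliges action. Here everything hangs on one look at fewer than a third of the patients, and on a word that can be read in two very different ways. On a formal reading, only a very large difference would be called an association, and a clean result could be taken as reassurance that 25 patients cannot give. On an informal reading, chance imbalances would often set off a re-evaluation. On either reading, an excess of aspiration, laryngospasm or other airway harm that emerges after patient 25 has no planned by-arm review until the final analysis. This affects participants' safety, and also what the trial can say about the safety of either airway.

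**Working it through.** **1. The plan's own figure.** The inputs are a margin of 0.5 h and an SD of 0.9 h; alpha and power are not stated. With one-sided alpha 0.05, power 80% and no true difference, n per arm = 2 × 0.9² × (1.645 + 0.842)² / 0.5² ≈ 40.1, rounded up to 41, or 82 in all. Adding 5% drop-out gives 82 / 0.95 = 86.3, rounded up to 87. The stated 82 and 87 are reproduced. The size was set for procedure time, not for harms.

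**2. Patients after the look.** 87 − 25 = 62 (62/87 = 71%). If 44 per group are enrolled, 88 − 25 = 63 (63/88 = 72%).

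**3. Arm sizes at the look.** About 12 v 13, assuming near 1:1 allocation. Blocking is not stated.

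**4. Reading A: association means a two-sided Fisher exact test at 0.05 (assumed).**
- 4/12 v 0/13: p = C(12,4)/C(25,4) = 495/12,650 = 0.039. The opposite table has probability 715/12,650 = 0.057, which is larger, so it is not added.
- 5/13 v 0/12: p = (1,287 + 792)/53,130 = 0.039.
- One event fewer fails: 3/12 v 0/13 and 4/13 v 0/12 both give p = 0.096.

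The smallest significant splits against zero are therefore 33% v 0% and 38% v 0%.

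**5. Chance of detection under Reading A.** The documents give no event rates, so 5% v 20% and 5% v 30% are assumed. The probability is the sum, over all significant tables in the direction of the true excess, of the product of the two binomial probabilities. Where the arms are unequal, the lower figure applies if the larger arm has the higher rate.

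| Enrolled | Arms | 5% v 20% | 5% v 30% |
|---|---|---|---|
| 25 | 12 v 13 | 6–11% | 21–31% |
| 50 | 25 v 25 | 20% | 55% |
| 75 | 37 v 38 | 39–48% | 80–85% |
| 87 | 43 v 44 | 48–56% | 86–89% |

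Relaxing the test to two-sided 0.10 raises the 5% v 20% figure at 25 patients only to 15–26%.

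**6. What a clean look means.** With no events in 13 patients, the one-sided 95% upper limit on the rate is 1 − 0.05^(1/13) = 0.206, about 21%. For 12 patients it is 22%.

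**7. Reading B: association means at least one event in one arm and none in the other.** With the same true rate of 5% in both arms:
- events only in the arm of 13: (1 − 0.95¹³) × 0.95¹² = 0.487 × 0.540 = 0.26;
- events only in the arm of 12: (1 − 0.95¹²) × 0.95¹³ = 0.460 × 0.513 = 0.24.

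Together, about half of such looks would show the pattern with no true difference.

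**The case against.** The strongest reply is that both airways are described as standard of care, that patients at high risk of aspiration are excluded, and that in a single-centre trial of 87 a light plan is proportionate. Later looks would themselves have limited power: 20% at 50 patients and 39–48% at 75 for 5% v 20%. That stands as far as power goes, and the dates 50 and 75 are not derived from anything in the plan. The case for more looks is continued review, not a powerful test.

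Several stronger readings are tempting, and the documents do not support them:

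- *A single aspiration triggers nothing, and only an extreme difference can count.* This follows only under a formal test, which the plan does not name. The firm defect is that the term is undefined.
- *All adverse outcomes are pooled, so minor events can mask serious ones.* No pooling is stated, and the data items are listed separately. The plan simply does not say which outcomes are compared or whether they are combined.
- *The DSMP and item 9 flatly contradict each other.* One denies specified criteria for stopping or changing the protocol; the other promises that the design will be re-evaluated, which is not the same as changed. They can be read together, but a reader cannot tell what obliges action.
- *Later events will go unreviewed.* The documents are silent on later by-arm review and do not exclude it. Data entry continues throughout, and the text available shows no answer to the item on provisions for adverse events, so nothing can be concluded from that gap.

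**Conclusion.** The point holds as a weakness in a stated rule that is cheap to repair. The only planned between-arm safety review before the final analysis takes place at 25 patients, and about 71% of enrolment follows it. The trigger is either nearly blind (6–11% detection for 5% v 20%) or often false (26% and 24% in the two directions under equal 5% rates), depending on a definition that the plan does not give. A look with no events in an arm of 13 still allows a rate of up to 21%.

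The split of 12 v 13, the Fisher test and all event rates are assumptions. The number of patients after the look and the lack of a definition come straight from the documents. The plan should be amended; nothing here shows that the trial is unsafe.

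**What to change.** Amend DSMP Details, item 1, and align Risks, item 9:

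1. Keep the look at 25 and repeat the cumulative by-arm table of adverse outcomes afterwards, for example at 50 and 75 enrolled, using items already collected under the HIPAA section.
2. State which outcomes are tabulated. Put serious airway and respiratory events on separate lines, and give counts with exact confidence intervals.
3. Count events in patients withdrawn after conversion under their randomised arm, so that the table does not lose airway failures.
4. State that each serious airway or respiratory event is reported to the IRB as it occurs, not only through an association.
5. Reconcile item 9 with the DSMP so that both give the same trigger and action.

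The added looks should cover adverse outcomes only, in which case they add no error to the primary comparison. That assurance does not extend to the existing look at 25, which includes the primary outcome.

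The cost is revised wording and two short tables from data already being entered, with no extra patients or procedures. The downside is a little more reporting work and a somewhat higher chance of reviewing a chance imbalance.
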